IRB Application for Population Health and Quality Research Study

Title of Study: rhBMP-2 versus Vivigen, a novel cellular allograft, in lumbar fusion procedures: a prospective randomized controlled study

Background and Statement of Context

Instrumented lumbar fusion procedures with bone graft are one of the most common procedures performed today. There are numerous bone graft options, including iliac crest bone graft, local autograft, allograft, extenders, and rhBMP [1]. Several studies have demonstrated the efficacy and complications associated with these bone graft options [2-6]. Iliac crest autograft, long considered the gold standard of bone graft, is associated with donor site morbidity, longer operative times, and limited availability [7]. Recombinant human bone morphogenetic protein-2 (Infuse) has revolutionized lumbar fusion surgery. Initially approved for a single level ALIF, Infuse has been utilized in many off-label applications. Further studies of Infuse demonstrated multiple adverse effects, such as osteolysis, ectopic bone formation, retrograde ejaculation, and potentially carcinogenesis [8]. The premium cost and adverse effects of Infuse has led researchers to develop other options. A novel bone graft option is the cellular allograft, a cryopreserved mixture of viable bone cells, demineralized bone matrix, and cancellous bone chips. This product is purported to be osteogenic, osteoinductive, and osteoconductive. There is a paucity of literature evaluating these cellular allograft bone graft options in lumbar spine surgery. This study is aimed at comparing the overall efficacy (clinical and radiographic) of Vivigen, a novel cellular allograft product, and rhBMP-2 when utilized in lumbar fusion procedures.

Study Questions/Objectives and Hypothesis

The purpose of this study is to compare the overall efficacy (clinical outcome and radiographic fusion) of Vivigen (cellular allograft product) and rhBMP-2 in patients who undergo a single level lumbar instrumented fusion. Specifically, when compared to their control group counterparts treated to rhBMP-2, we hypothesize that the intervention group administered Vivigen would, following surgery, experience:

1. Comparable mean postoperative leg/back pain score, where the pain scores are obtained using the numeric rating scale of 0-no pain, to 10-worst pain possible
2. Comparable inpatient length of stay (LOS)

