3. Comparable postoperative Oswestry Disability Index (ODI) score (0-no disability, to 100-maximum disability possible), two weeks, 6 weeks, 3 months, 6 months, and 1 year postoperatively
4. Comparable fusion rates, evaluated via CT scan 1 year postoperatively

Study Benefits to Virtua

Virtua could stand to gain some significant cost savings if the more cost-effective Vivigen is shown to be a clinically equivalent bone graft option that can replace the more expensive rhBMP-2.

Study Methodology

Patients who meet all of the following inclusion criteria may be eligible to participate in the study if:

1. Age 18 or older;
2. Diagnosed with lumbar degenerative/isthmic spondylolisthesis, degenerative disc disease with axial low back pain and neurologic symptoms, failed conservative treatment and eligible for a single level lumbar instrumented fusion;
3. Willing to provide informed consent, participate in study, and comply with study protocol.

Patients who meet any of the following criteria may not be eligible to participate:

1. Pregnant or contemplating pregnancy prior to surgery;
2. Serious spinal conditions (e.g. spinal cord compression, cauda equina syndrome, spinal infection, spinal tumor, spinal fracture, inflammatory or systemic spinal arthritis);
3. Surgery involving more than 2 vertebral levels;
4. Worker's compensation or personal injury related to lumbar spine (treatment outcomes may be affected by patient's personal interests; could also run into potential issues with reimbursement).
5. Lactating women
6. Patients who have a known or suspected allergy to Gentamicin Sulfate, Meropenem, Vancomycin, Dimethyl Sulfoxide (DMSO), and Human Serum Albumin
7. Immune compromised patients

During the preoperative office visit, the surgeon will inform patients that appear to meet study eligibility criteria, about the study, and discuss the differences between the two bone graft options, including their potential risks and benefits. The surgeon will make clear to the patient that consenting to be a part of the study means that the patient has agreed to be randomly assigned to one of the two bone graft groups.

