Patients who are deemed eligible to participate in the study and are willing to participate will be asked by a trained study physician assistant (PA) to complete the research informed consent. This document will be summarized verbally by the PA and potential participants will be given the opportunity to ask questions about the protocol or their involvement prior to providing consent. Those who agree to

participate and provide research informed consent will be enrolled in the study, and given a copy of the research informed consent document. The patient's informed consent would be added to the patient's chart.

A computer generated randomization scheme will be employed and the randomization outcomes will be sealed in envelopes. On the day of surgery, in the operating room, the circulating nurse will pick an envelope from the randomized stack, unseal the envelope, and based on the outcome (even or odd), assign the patient to one of the two bone graft groups. While the study intervention group (even) will receive 5cc Vivigen and local autograft, the control group (odd) will receive small kit rhBMP-2 with local autograft. Anesthesiologists will use their usual pre-operative and intra-operative techniques for all study participants.

The surgical team, including the surgeons, will be blinded to the treatment options until decompression/instrumentation have been completed. The patients and all staff, including hospital nursing staff, case management, and physical therapists, will be blinded as to which bone graft treatment the patient received.

The primary outcome in this study will be the mean Oswestry Disability Index (ODI) score. The ODI is one of the most commonly utilized condition-specific measures of disability used in the management of spinal disorders [9]. The ODI Version 2.0 is what the Virtua Memorial Spine Center currently uses to examine patient disability preoperatively, as well as two weeks, 6 weeks, 3 months, 6 months, and 1 year postoperatively. The ODI has 10 sections of six statements with the first statement corresponding to a score of 0 indicating no disability and the last statement corresponding to a score of 5 indicating maximum possible disability. The final score which is calculated as: $[\text{total score}/(5 \times \text{number of questions answered})] \times 100\%$, could range from 0% to 100% [9].

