Adopting a standard deviation of 10, which is one of the most commonly used standard deviations in ODI studies [9], and looking to detect a mean difference of 8 in ODI scores to indicate superiority of one bone graft option over the other, it is estimated that for a statistical power of 80% and significance level of 0.05, a minimum of 26 participants will be required in each study group for a total of 52 study participants. To minimize the possibility of dropouts or incomplete data impacting the analysis, a minimum of 30 participants will be enrolled in each study group, for a total of 60 study participants.

Secondary outcome measures in this study include the mean scores from the 36-Item Short Form Survey Instrument (SF-36) [10]; the mean leg/back pain scores from the numeric rating scale of 0-no pain, to 10-worst pain possible; mean LOS; incidence of ORAEs, and fusion rates examined via CT scan 1 year postoperatively by an independent radiologist.

Means will be compared between the two study groups using one-tailed 2-sample t tests, proportions will be compared using chi-square tests, and logistic regression will be used to analyze for confounding effects. All statistical analyses will be conducted in Minitab 16 Statistical Software.

Protection of Human Subjects

Throughout the study, the principal investigators (Virtua Memorial spine surgeons and PAs), will be the only ones with access to the data collection database. Following the completion of the study, all personal health information collected, including name, gender, age, significant medical comorbidities, and postoperative complications, will be de-identified as soon as possible prior to data analysis and any subsequent publications or research submissions. Patient would be told participation is purely voluntary with no monetary reimbursement and minimal risk of being assigned to one of the two pain management groups.

References

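### The hypotheses are that Vivigen is comparable to rhBMP-2, but the trial is sized and tested for superiority, with no margin or confidence-interval rule that could establish comparability

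*Combined protocol and SAP*

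**What the plan says.** Under Study Questions/Objectives and Hypothesis, the protocol states that "we hypothesize that the intervention group administered Vivigen would, following surgery, experience" comparable results on four outcomes: pain, length of stay, ODI and fusion. The two that matter most here are "Comparable postoperative Oswestry Disability Index (ODI) score", listed at five postoperative times, and "Comparable fusion rates, evaluated via CT scan 1 year postoperatively".

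Study Benefits to Virtua describes the possible cost saving "if the more cost-effective Vivigen is shown to be a clinically equivalent bone graft option that can replace the more expensive rhBMP-2".

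Study Methodology names the endpoint: "The primary outcome in this study will be the mean Oswestry Disability Index (ODI) score". The sample-size paragraph then changes the question. "Adopting a standard deviation of 10", it describes the investigators as "looking to detect a mean difference of 8 in ODI scores to indicate superiority of one bone graft option over the other". With 80% power and a significance level of 0.05 this gives 26 per group, raised to 30 to allow for dropout and incomplete data. The analysis paragraph reads: "Means will be compared between the two study groups using one-tailed 2-sample t tests, proportions will be compared using chi-square tests". It gives neither the direction of the one-tailed tests nor a null value other than zero.

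The document contains no equivalence or non-inferiority margin, no confidence-interval criterion, and no definition of comparable for any outcome.

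**The concern.** A test of no difference can show that two grafts differ. It cannot show that they are comparable, because a non-significant result is also what a small or noisy trial produces when a real difference exists. The hypotheses and the sample-size paragraph therefore ask different questions, and only the superiority question has a planned answer.

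If a non-significant p-value were taken as support for the hypotheses, the incentives would run the wrong way: dropout, missing data and measurement noise would all make the hoped-for result easier to obtain. What is at stake is the central reading of the primary outcome and, through it, a decision to replace one graft with another. A margin chosen after the data are seen would not be credible, so the gap has to be closed in advance.

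**Working it through.** **Inputs from the sample-size paragraph.** Difference 8 ODI points (higher is worse), SD 10, power 80%, significance level 0.05, 26 per arm required and 30 enrolled. Results below are given as 26 / 30 per arm. **Assumptions not in the plan:** margins other than 8, SDs other than 10, the true differences, and the fusion rates.

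**1. The plan's own figure.** Power of the two-sample t test comes from the noncentral t distribution with df = 2n − 2 and noncentrality δ / (SD·√(2/n)). At n = 26 the noncentrality is 8 / (10·√(2/26)) = 8 / 2.77 = 2.88. Two-sided 0.05 power is 80.7%, and 26 is the smallest n that reaches 80%. One-tailed, 21 per arm would suffice. The stated N is thus a two-sided superiority calculation, correct for that purpose.

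**2. Reading non-significance as comparable.** Chance of a non-significant result when Vivigen is truly worse:

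| Test at 0.05 | 8 points worse | 5 points worse |
|---|---|---|
| One-tailed, harmful direction | 11.5% / 8% | 45% / 39% |
| Two-sided | 19% / 14% | 58% / 52% |
| One-tailed, opposite direction | over 99.9% | over 99.9% |

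The last row is included only because the direction is not stated.

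**3. A borderline result at 30 per arm.** The standard error is 10·√(2/30) = 2.58. The one-tailed threshold is 1.672 × 2.58 = 4.32, and the 95% half-width is 2.002 × 2.58 = 5.17. An observed disadvantage just under 4.32 is non-significant, yet its 95% interval runs from 4.32 − 5.17 = −0.85 to 4.32 + 5.17 = about 9.5. That does not exclude the plan's own 8 points.

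**4. Non-inferiority instead.** One-sided 0.025, true difference 0, with the margin in place of δ:

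| Margin | SD | Power (26 / 30) | n per arm for 80% |
|---|---|---|---|
| 8 | 10 | 80.7% / 86% | 26 |
| 6 | 10 | 56% / 63% | 45 |
| 5 | 10 | 42% / 48% | 64 |
| 4 | 10 | 29% / 33% | 100 |
| 8 | 12 | 65% / 72% | 37 |
| 8 | 15 | 47% / 53% | 57 |

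If Vivigen is truly 2 points worse, a margin of 8 leaves an effective distance of 8 − 2 = 6, so power is 56% / 63%.

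**5. Equivalence within ±8 instead.** Two one-sided tests, true difference 0, SD 10. Requiring the 90% interval to lie inside ±8 gives 77% / 84%, with 28 per arm needed for 80%. Requiring the 95% interval to do so gives 62% / 72%, with 34 per arm needed.

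**6. Fusion, for illustration only.** With 27/30 fused in both arms, the Newcombe 95% interval for the difference is ±17 percentage points; with 24/30 in both arms it is ±20. A non-significant chi-square test at this size leaves large differences open.

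**The case against.** The stated purpose is simply to compare the two grafts, and the benefits sentence is a conditional cost rationale, not an objective. A test for superiority of either graft is a legitimate design. The protocol never says that a non-significant result will be reported as comparable, and it gives no null value, so a shifted null is not strictly ruled out. The sample size may also be adequate: the same 26 per arm gives 80.7% power for non-inferiority if 8 points is the margin.

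Some of this stands. The benefits sentence is context; the mismatch rests on the four hypotheses. The misuse of a p-value is an inference, and the rates in step 2 of the working depend on it. The trial is not shown to be too small. Nor is non-inferiority the only remedy, since the investigators could keep the superiority design and change what they claim.

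None of it supplies the missing criterion. The sample-size text speaks of superiority, which makes zero the natural null value, and no passage says what result would count as comparable. The figure of 8 also needs care: the plan offers it as a difference large enough to indicate superiority, and it does not follow that a loss of that size is tolerable.

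**Conclusion.** The concern holds and must be fixed before the data are analysed. The hypotheses are about comparability, the design and tests are about superiority, and no prespecified rule connects them, so the analysis as written cannot establish what is hypothesised. This follows from the text and needs no assumption.

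The size of the consequence rests on SD 10 and on the inferred reading of non-significance. On that basis, an 8-point disadvantage would pass in 11.5% of trials at 26 per arm and 8% at 30 with the most favourable one-tailed direction, against 2.5% under a non-inferiority rule with that margin. Whether 60 patients are enough depends on the margin: they are at 8 points with a true difference of 0, and they are not at 6 or below.

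**What to change.** **Preferred change.** Restate the primary ODI analysis as non-inferiority of Vivigen and replace the superiority wording in the sample-size paragraph. Suggested text:

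*The primary analysis will estimate the difference in mean ODI (Vivigen minus rhBMP-2) at [one named time point], with a two-sided 95% confidence interval. Vivigen will be declared non-inferior only if the upper limit is below [margin], justified as follows: [reasons]. Fusion and the other secondary outcomes will be reported as differences with 95% confidence intervals. A non-significant t test or chi-square test will not be reported as showing comparability.*

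The investigators must choose the time point, because five are listed and none is named as primary.

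**Alternatives.**
- Equivalence: require the 90% confidence interval to lie within ± a margin that is likewise prespecified and justified. If the 95% interval is required, state the lower power or raise N.
- Keep the superiority design: reword the hypotheses and the benefit statement so that no claim of comparability or equivalence is made.

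**Cost.** If 8 points is justified as a non-inferiority margin, with SD 10 and a true difference of 0, N stays as planned and only the text changes; state the power of 80.7% at 26 per arm and 86% at 30. A margin of 6 needs 45 evaluable per arm, and a margin of 5 needs 64. Equivalence within ±8 needs 28 evaluable per arm with a 90% interval (above the 26 planned as evaluable, within the 30 enrolled) or 34 with a 95% interval (above the 30 enrolled). The real price is that a margin must be defended in advance, and fusion can be claimed only as precisely as its interval allows.

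### Enrolling 30 for 26 per group protects power only; with a plain t test and no rule for missed ODI visits, loss linked to poor recovery can bias the primary comparison

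*Combined protocol and SAP*

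**What the plan says.** All the relevant text is in the Study Methodology section of the combined protocol and SAP.

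- Outcome: "The primary outcome in this study will be the mean Oswestry Disability Index (ODI) score". ODI is taken preoperatively and at "two weeks, 6 weeks, 3 months, 6 months, and 1 year postoperatively". No visit is named as primary.
- Sample size: SD 10, a difference of 8 points, 80% power and a significance level of 0.05 give 26 per group. The sole statement on attrition follows: "To minimize the possibility of dropouts or incomplete data impacting the analysis, a minimum of 30 participants will be enrolled in each study group".
- Analysis: "Means will be compared between the two study groups using one-tailed 2-sample t tests". Logistic regression is planned for confounding.

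The plan defines no analysis population, missing-data assumption, imputation, longitudinal model or sensitivity analysis. The ODI formula divides by the number of items answered, so it deals with skipped items but not with a missed questionnaire. Logistic regression for confounding is not a missing-data method.

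**The concern.** The over-enrolment sentence treats a question of bias as a question of numbers. If patients who recover badly are the ones who stop returning, the group mean at a late visit is too favourable however many patients remain. A t test at 1 year gives no weight there to a patient who had poor scores at 3 and 6 months and then left, although up to four postoperative scores for that patient are on file.

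What is at stake depends on the truth. If one graft is worse and loses its poor recoverers, the estimated difference shrinks towards the comparable result that the hypotheses expect and on which the stated cost-saving benefit rests. If the grafts are equal and one group alone loses poor recoverers, a false difference can appear instead.

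**Working it through.** **Inputs.** From the Study Methodology section: SD 10, difference 8, power 80%, significance level 0.05, 26 per group needed, 30 enrolled. Assumed, because the documents are silent: normally distributed ODI, and which patients are lost.

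**1. The plan's own figure.** Normal approximation, two-sided: n = 2(1.960 + 0.842)² × 10² / 8² = 24.5, so 25. The exact two-sided t calculation gives 26 per group with power 80.7%, which matches the plan. The allowance is 4/30 = 13.3% per group, and 26 / (1 − 4/30) = 30. (A one-sided test would need 21 by the t calculation. That the plan's 26 fits a two-sided test while its tests are one-tailed is a separate matter.)

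**2. What losing 4 of 30 does to one group's mean.** Error in the retained mean = −(share lost) × gap, where the gap is the mean ODI of those lost minus that of those retained.

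- Gap 10: (4/30) × 10 = 1.3 points.
- The four worst of 30: at SD 10 the expected gap to the other 26 is 17.9 points, so (4/30) × 17.9 = 2.4 points.
- Gap needed to hide the whole target: 8 / (4/30) = 60 points.

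**3. Simulation with exactly 26 v 26 analysed** (100,000 trials per row, SD 10). One group loses 4 patients drawn from its worst 15, 10 or 4; the other loses 4 at random. In the middle columns the group losing poor recoverers is truly 8 points worse. In the last column there is no true difference, and the false positives counted are those favouring that group.

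| Loss in the one group | Shift | Share of 8 | True 8 estimated as | One-sided power | One-sided false positives |
|---|---|---|---|---|---|
| 4 at random | 0.0 | 0% | 8.0 | 88% | 5% |
| 4 of worst 15 | −1.2 | 15% | 6.8 | 79% | 11% |
| 4 of worst 10 | −1.6 | 20% | 6.4 | 75% | 14% |
| 4 of worst 4 | −2.4 | 30% | 5.6 | 69% | 25% |

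When both groups lose 4 patients from the worst 10, or the worst 4, of their own group, the shift is about zero.

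**4. One common rule in both groups.** Here the chance of loss rises with the patient's own ODI along the same logistic curve in both groups. With no true difference, the estimated difference is about 0. With a true difference of 8, the worse group loses more patients because its scores are higher:

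- Slope 1 logit per SD: estimate 7.5, with 13% v 7% lost.
- Slope 2 logits per SD: estimate 6.6, with 18% v 7% lost. The 18% is above the plan's allowance.

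**5. What the earlier visits recover.** With dropout made to depend on the last observed ODI, a true difference of 8 and within-patient correlation 0.4, 0.6 or 0.8, the difference among completers averaged 7.21, 6.95 and 6.52. A likelihood analysis using the earlier visits averaged 7.97, 8.10 and 7.93. Loss here was about 13% v 30%, well above the plan's allowance, so this run shows what the remedy can do and does not measure the bias with 26 left per group.

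**The case against.** - **The bias is conditional.** A reader might infer that the primary comparison is bound to be biased. It is not: with no true difference and the same loss rule in both groups, the shift is about zero. The plan hypothesises comparable ODI and blinds patients, which makes group-specific loss less likely. This stands. Blinding does not, however, remove loss driven by a real graft effect (step 4).
- **The size is limited.** It is tempting to suppose that the four lost patients are 30 points worse, which would hide (4/30) × 30 = 4.0 points, half the target. At the plan's SD of 10, a gap of 30 arose in about 0.02% of simulated groups even when the four worst always left. The documents do not support that figure.
- **Analysis of attenders only is inferred.** The plan does not mention completers or per-visit tests. The inference is fair, since a 2-sample t test with no rule for missing scores uses the scores that exist. It would be too strong to say that a leaver's earlier scores are thrown away altogether: the third hypothesis covers all five postoperative visits, so those scores would count at their own visits.
- **The direction is not fixed.** A pull towards comparability needs the worse graft to lose its poor recoverers and a non-significant result to be read as comparability. The last column of the table shows the opposite risk.
- **The likelihood model does well partly by construction.** In step 5, loss depended only on observed scores, the condition under which such a model is unbiased. This stands, and is why a sensitivity analysis is also needed. Multiple imputation using baseline and earlier ODI would be an acceptable alternative.

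**Conclusion.** The point holds in conditional form. Over-enrolment protects sample size and power, and the plan contains nothing that protects the ODI comparison from informative loss. With 26 v 26 analysed, loss of poor recoverers in one group and random loss in the other shifts the difference by about 1.2 to 2.4 points (15% to 30% of the 8-point target). The shift is about zero if loss is alike in both groups and there is no true difference. These sizes rest on the plan's SD of 10, normal scores and assumed loss patterns; the documents give no expected dropout rate or reasons for loss. The documents do not show that bias will occur, that it must favour comparability, or that it could hide most of the target. The change is worth making because the scores it needs are already scheduled, and because a missing-data rule chosen after outcomes are known would be post hoc.

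**What to change.** 1. Name one primary ODI visit, for example 1 year, the last scheduled visit.
2. Make the primary ODI analysis a repeated-measures likelihood model (MMRM) of all scheduled postoperative ODI scores of every randomised, grafted patient, with treatment, visit, treatment-by-visit and baseline ODI. Read the treatment contrast at the primary visit.
3. Keep the 2-sample t test at that visit as a supportive analysis.
4. Add a delta-adjusted (tipping-point) sensitivity analysis, because the model corrects only loss explained by observed scores. Record reasons for loss by group to inform it.
5. Reword the over-enrolment sentence to say that 30 per group protects sample size and power only.

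The 26 and 30 per group need not change on this account. The cost is SAP wording and a little more analysis work, plus another program for this one analysis if Minitab 16 does not fit the model.

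### The analysis uses one-tailed t tests with no stated direction, although the aim runs both ways and 26 per group is the two-sided sample size

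*Combined protocol and SAP*

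**What the plan says.** The statements that bear on this point are spread over three parts of the combined protocol and SAP.

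- **Sample size (Study Methodology).** The primary outcome is mean ODI. The calculation starts with "Adopting a standard deviation of 10" and is described as "looking to detect a mean difference of 8 in ODI scores to indicate superiority of one bone graft option over the other". It concludes that "for a statistical power of 80% and significance level of 0.05, a minimum of 26 participants will be required in each study group". Enrolment is then raised to 30 per group to allow for dropout. The sidedness of the 0.05 is not given.
- **Analysis (Study Methodology, shortly after).** "Means will be compared between the two study groups using one-tailed 2-sample t tests". No tail is named for ODI or for any other mean.
- **Objectives.** The ODI hypothesis under Study Questions/Objectives and Hypothesis is "Comparable postoperative Oswestry Disability Index (ODI) score". Study Benefits to Virtua looks ahead to the case where "Vivigen is shown to be a clinically equivalent bone graft option". Neither says that one graft is expected to do better, and no margin is given.

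**The concern.** A one-tailed test is not defined until its direction is fixed. Here the only aim attached to the sample size is "to indicate superiority of one bone graft option over the other", which allows either graft to win, and the listed hypotheses allow neither to. Nothing tells the analyst which tail to use.

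The consequence depends on how that gap is filled:

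- If the tail is chosen after seeing which group did better, the nominal 5% test has a 10% type I error.
- If the tail is fixed at Vivigen better, a worse ODI with Vivigen cannot be declared, however large. This matters for a product being considered as a replacement.
- If it is fixed at Vivigen worse, a better ODI with Vivigen cannot be declared.

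Either fixed tail serves only half of the stated aim. The sample size also looks like that of a two-sided test, which would mean that the trial was sized for one test and will be analysed with another. The analysis sentence covers all means, so the SF-36, pain scores and length of stay have the same gap.

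**Working it through.** **Inputs, all from the sample size paragraph of Study Methodology.** SD 10; difference 8, so d = 8/10 = 0.8; power 80%; level 0.05; two equal groups of n.

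**Method.** For the equal-variance two-sample t test, df = 2n − 2 and the noncentrality is d × √(n/2). Power is the probability that a noncentral t variable passes the critical value, which is t(0.975, df) in absolute size for a two-sided 0.05 test and t(0.95, df) for a one-tailed 0.05 test.

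**Step 1. Reproduce the plan's 26.**

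| n per group | Two-sided 0.05 | One-tailed 0.05, tested direction |
|---|---|---|
| 20 | 69.3% | 79.9% |
| 21 | 71.6% | 81.7% |
| 25 | 79.1% | 87.4% |
| 26 | 80.7% | 88.5% |
| 30 | 86.1% | 92.2% |

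The smallest n reaching 80% is 26 two-sided and 21 one-tailed. The stated 26 is the two-sided figure exactly. The normal approximation, n = 2 × [(z for alpha + z for power)/d]², gives the same contrast: 2 × [(1.960 + 0.842)/0.8]² = 24.5, so 25, two-sided; and 2 × [(1.645 + 0.842)/0.8]² = 19.3, so 20, one-tailed.

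**Step 2. Smallest significant difference.** This is t × 10 × √(2/n).

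- n = 26: standard error 10 × √(2/26) = 2.774. Two-sided 2.009 × 2.774 = 5.57; one-tailed 1.676 × 2.774 = 4.65.
- n = 30: standard error 10 × √(2/30) = 2.582. Two-sided 2.002 × 2.582 = 5.17; one-tailed 1.672 × 2.582 = 4.32.

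**Step 3. A worked case.** Take an observed ODI difference of 5 points at 26 per group with SD 10. Then t = 5/2.774 = 1.803 on 50 df. The two-sided p is 0.077. The one-tailed p is 0.039 if the difference lies in the tested tail, and 1 − 0.039 = 0.961 if it lies in the other.

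**Step 4. Power in the untested direction.** With a true 8-point difference the other way, n = 26 and noncentrality −0.8 × √13 = −2.884, the one-tailed test rejects with probability 0.0000035, about 0.0004%. The two-sided test keeps 80.7% in either direction.

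**Step 5. Tail chosen from the data.** Under no difference, each tail rejects 5% of the time and the two events exclude each other, so the type I error is 0.05 + 0.05 = 0.10.

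**The case against.** The strongest reply is that no figure in the plan is wrong. The plan asks for a minimum of 26, which exceeds the one-tailed requirement of 21, so the planned test has more than 80% power in its tested direction. A one-tailed test with its direction fixed beforehand keeps the 5% error rate, and no sentence says that the tail will be picked from the data. That the sizing was two-sided is an inference; a one-sided test at 0.025 would also give 26.

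Much of this is right. The trial is not underpowered, and the 10% error is conditional on a choice that the plan leaves open. But the plan states 0.05 and mentions 0.025 nowhere. Even with the inference about sizing set aside, the missing direction and the clash with a two-directional aim remain.

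Two limits on the size of the effect also stand. With a fixed tail, the lower threshold applies in the tested direction only. And the 5-point example is one of a narrow set: at 26 per group, only observed differences between 4.65 and 5.57 points in the tested direction switch from non-significant to significant.

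A further objection is that two-sided testing is not the only repair. A one-sided non-inferiority test with a justified margin would suit the comparability hypotheses better. A non-significant two-sided superiority test must not be read as evidence of comparability, and its lower power (80.7% against 88.5% with the tail at Vivigen worse) makes such a misreading easier to reach. That is a reason to settle comparability separately. It does not rescue a one-tailed superiority test without a direction, and the plan sets no margin.

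**Conclusion.** The concern holds, and it should be corrected before analysis. The defect is in the specification of the primary test and its conflict with the plan's own aim and sizing. It is not a miscalculated or insufficient sample size.

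As written, the test either cannot answer half of the stated question (power about 0.0004% in the untested direction) or, if the tail follows the data, runs at 10% type I error. Where the tail is fixed, the threshold in the tested direction is about 0.9 points lower than in the two-sided test that the sample size matches: 5.57 − 4.65 = 0.92 at 26 per group and 5.17 − 4.32 = 0.85 at 30.

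The figures assume the plan's SD of 10, equal group sizes and the equal-variance t test. The two-sided basis of the 26 is inferred from the exact match. The absence of a direction is read directly from the text.

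**What to change.** Make two wording changes before analysis.

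1. In the analysis sentence, specify two-sided two-sample t tests at the 0.05 level, reported with 95% confidence intervals for the differences.
2. In the sample size sentence, call the 0.05 a two-sided significance level.

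Keep 26 per group and 30 enrolled. No patients are added. The price is a stricter threshold (5.57 instead of 4.65 points at 26 per group) and 80.7% instead of 88.5% power in a single pre-chosen direction. The stated 80% target is still met.

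This repair serves the superiority aim only. If the sponsor wants to conclude that the grafts are comparable or clinically equivalent, the plan needs a non-inferiority or equivalence analysis with its own justified margin and a fresh sample size check. The 8 points in the present calculation is a difference to detect and should not be reused as that margin without justification. That is separate work, beyond these two edits.
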